#### 2 STUDY OBJECTIVES

- **2.1** Primary Objectives
- 2.1.1 Develop IntelliCare and optimize its functionality through laboratory and field usability testing.
- 2.1.2 Develop the machine learning models and algorithms that will continuously learn from user interactions with IntelliCare to provide intervention recommendations and motivational messaging.
- 2.1.3 Conduct a randomized controlled trial (RCT) comparing 8 weeks of IntelliCare with the machine learning component to 8 weeks of IntelliCare without the machine learning component for the treatment of depression and anxiety. Participants will be evaluated at baseline, week 4, week 8, and at 3- and 6-month post-treatment follow-ups. It is hypothesized that 1) IntelliCare with the recommendations, in contrast to IntelliCare without the recommendations, will produce greater adherence and greater reductions in depressive and anxiety symptoms and 2) IntelliCare with coaching will produce greater greater adherence and greater reductions in depressive and anxiety symptoms. The primary patient centered outcome will be depression/anxiety severity.
- 2.2 Secondary Objectives.
- 2.2.1 Exploration of the mediating effects of adherence markers (e.g. time in treatment, app launches, etc.) coaching variables (e.g. message frequency, timing, etc.), and psychological variables (e.g. change in self-report measures) on depression and anxiety outcomes.
- **2.2.2** Exploration of moderating variables on outcomes, such as baseline demographics, baseline characteristics.
- 2.2.3 Explore, optimize, and validate coaching methods.

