At the end of the 8 week intervention, all participants will be informed that they may continue using the IntelliCare system on their phones but participants in groups 1 and 3 will no longer have access to their coach. For any participants who do continue app use after the study period has ended, the IntelliCare system will continue to collect app data as before.

4.1.6.1 Phase III Assessment, measures and compensation. RCT participants will receive trial assessments at baseline, week 4, and week 8 (post-treatment). Post-treatment follow-up evaluations will occur at 3 and 6 months to evaluate maintenance of gains. Assessments will consist of telephone based interviews and online self-report questionnaires. All assessments and evaluations will be conducted by an RA (i.e. coaches will not perform assessments on patients they coach). Depression will be measured at baseline by telephone interview using the MINI MDE module. Self-reported depression will be measured at baseline, wk4, wk8, 3 months post-treatment and 6 months post-treatment using the PHQ-9 administered online. Self-reported anxiety will be measured using the GAD-7 administered online at

baseline wk4, wk8, 3 months post-treatment and 6 months post-treatment. *Adherence* will be assessed through app use data from phone, including number of times the apps were accessed, number of times each app feature was accessed and percentage of messages viewed. Participants will be paid up to \$40 for the screening/baseline assessments, \$30 for the week 4 and 8 assessments, and \$30 for the 3 and 6 month assessments (total= up to \$160). Participants will not be compensated for using the apps or communicating with the study coach. Payments may be made in either Amazon credits or by check depending on participant preference, NU payment policies, and payment availability at the time of study participation. Individuals recruited through Focus Pointe Global will be paid through PayPal by Focus Pointe Global.

**4.1.7** *Phase II Study Retention.* Communication from the research study may occur across a participant's involvement in the trial to increase participant retention. Such contact could include sending greeting cards via mail or email (thank you, birthday, etc.) or sending small tokens of appreciation (keychains, pens, stress balls).

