- 6.9.2 Preliminary data indicates that approximately 50% of patients stop participating in BITs (which we define here as "drop out") by week 7 (see Sec. D.1.1). A sample size of 135/arm (total sample of 270) will provide 80% power to detect a difference in median drop out time from 7 to 10 weeks. We estimate from existing data (Sec D.1.1) that a 3 week increase would result in an 11% improvement in depression severity (ES=0.30). Additionally, this sample provides 80% power to detect an increase in continued participation from 50% to 61.6% at week 7. Both analyses are based on a log-rank test at a type 1 error rate of 5%, with accrual of 54 weeks and 12 weeks of intervention. Power for continuous patient

centered outcomes were based on independent t-tests, and would have 80% power to detect effect sizes of 0.34. Power calculations were performed using Pass 2008.(Hintze, 2008)

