#### **6.10** Adherence Outcomes:

- 6.10.1 The primary outcome will be time to last use of a treatment element (lesson or tool), and will be tested between groups using traditional survival (Kaplan-Meier) methods, where the event of interest is last use from intervention start. Secondary analyses of the primary outcome would include Cox regression models that would adjust for potential effect modifiers or moderators such as gender, race, and age.
- **6.11** Patient Centered Outcomes:
- 6.11.1 Although power was presented for independent t-tests, primary analyses for patient centered outcomes (QIDS-C, MDD, and PHQ-9) will utilize generalized linear mixed (GLM) models (with link functions depending on the distribution of the outcome), that can examine patterns over the course of treatment and follow-up, and can account for missing data.(Gibbons et al., 1993)
- **6.12** Secondary Mediation Analyses:
- 6.12.1 Mediators will be entered into our models as time-varying covariates. We used the framework of Muller and colleagues(Muller, Judd, & Yzerbyt, 2005) to identify those variables, which mediate the effects of treatment on depression. Only if the 4 criteria specified by Muller are satisfied (treatment effect for depression, treatment effect for the mediator, effect of mediator on depression, and reduction of treatment effect when mediator is included), will we calculate the effect of mediation using MacKinnon and colleagues' product of coefficients method.(MacKinnon, Lockwood, Hoffman, West, & Sheets, 2002) Bias-corrected 95% confidence intervals for the mediated effect will be calculated using bootstrapping.(Shrout & Bolger, 2002)
- 6.12.2 Development of the recommendation engine algorithms will use machine learning and Baysean. statistical methods that will continuously learn that will continuously learn from user interactions with IntelliCare to provide intervention recommendations.
- **6.12.3** Exploration of moderating variables on outcomes, such as baseline demographics, baseline characteristics.
- 2.2.3 Explore, optimize, and validate coaching methods. This will include analyses of all data captured in the delivery of coaching, including the timing and content of messages and phone calls, and coach records related to participant encounters.

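### RCT symptom analysis (6.11.1): the mixed model does not use recorded app use for missing scores, so the coaching contrast is biased if response after stopping differs by coaching group

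*Combined protocol and SAP*

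**What the plan says.** Section 6.11.1 states that "primary analyses for patient centered outcomes (QIDS-C, MDD, and PHQ-9) will utilize generalized linear mixed (GLM) models", and describes these as models "that can examine patterns over the course of treatment and follow-up, and can account for missing data". That is all the RCT plan says about missing scores. It names no missingness assumption, auxiliary variable or sensitivity analysis.

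App use appears elsewhere, for other purposes. Adherence "will be assessed through app use data from phone" (4.1.6.1), and time to last use is the adherence outcome (6.10.1). For mediation, 6.12.1 says "Mediators will be entered into our models as time-varying covariates".

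The protocol also links use to coaching and to symptoms. Objective 2.1.3 hypothesises that "IntelliCare with coaching will produce greater greater adherence and greater reductions in depressive and anxiety symptoms". Section 6.9.2 reports that "approximately 50% of patients stop participating in BITs" by week 7, and estimates that "a 3 week increase would result in an 11% improvement in depression severity (ES=0.30" in effect-size units.

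Section 6.11.1 does not list GAD-7, although 4.3.1.1.2.1 makes it the anxiety measure among the patient-centred outcomes. The two lists need reconciling. The argument below applies to PHQ-9 as written, and to GAD-7 if it is analysed the same way.

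**The concern.** A likelihood-based mixed model gives unbiased group means only when the chance of a missing score depends on what the model contains: here, group and the scores already observed. App use is outside that set. On the protocol's own premises, stopping use goes with worse symptoms and is less common with coaching. PHQ-9 and GAD-7 are completed online, and coaching consists mainly of brief text messages to promote engagement (4.1.6), so it is plausible that response after stopping depends on having a coach. The observed scores in the two coaching groups would then contain different mixes of users and stoppers, and the model would carry that imbalance into the contrast.

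At stake is the symptom half of the second hypothesis in 2.1.3. The variable that could remove this source of bias is already being collected.

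**Working it through.** **The plan's own figures.** The documents give no figure for bias from missing data. The power figures in 6.9.2 do reproduce. Medians of 7 and 10 weeks give a hazard ratio of 7/10 = 0.70 if times are exponential. With 54 weeks of accrual, 12 weeks of intervention and 135 per arm, about 247 events are expected. Power = Φ(√247/2 × |ln 0.70| − 1.96) = Φ(0.84) = 80%. For the continuous outcomes, Φ(0.34/√(2/135) − 1.96) = Φ(0.83) = 79.8%.

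**Inputs from the documents.**
- Median time to last use of 7 and 10 weeks (6.9.2).
- 0.30 SD per 3 weeks = 0.10 SD per week of use (6.9.2).
- Treatment and the main symptom visit end at week 8 (2.1.3, 4.1.6.1).

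**Assumptions.**
- Exponential times, with the 7 and 10 weeks assigned to uncoached and coached. Section 6.9.2 does not make that assignment.
- A linear, causal effect of use, and no other coaching effect.
- Non-response u while still using (5%; 3% in the 22%/12% row) and q after stopping.

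**True effect through use.** With λ = ln 2/median, S = exp(−8λ) and mean weeks of use to week 8 = (1 − S)/λ:
- Uncoached: λ = 0.0990, S = 0.453, mean 5.525 weeks. Among stoppers, (5.525 − 8 × 0.453)/0.547 = 3.48 weeks.
- Coached: λ = 0.0693, S = 0.574, mean 6.141 weeks. Among stoppers, 3.63 weeks.
- Difference 0.615 weeks × 0.10 = 0.06 SD.

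**Effect seen among responders.** Responder mean = [8(1−u)S + s(1−q)(1−S)] / [(1−u)S + (1−q)(1−S)], where s is the stoppers' mean. For 45% versus 25%:
- Uncoached: (8 × 0.430 + 3.48 × 0.301)/0.731 = 6.139 weeks.
- Coached: (8 × 0.546 + 3.63 × 0.319)/0.865 = 6.388 weeks.
- Difference 0.249 weeks = 0.025 SD, or 0.249/0.615 = 40% of the true effect.

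The mixed-model column comes from large simulations with baseline, week 4 and week 8 scores. Observed scores recover little: the model stays within about 5 percentage points of the responder-only result.

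| Non-response after stopping, uncoached / coached | Week-8 scores missing | Responders only: SD (share kept) | Mixed model, share kept |
|---|---|---|---|
| 50% / 20% | 30% / 11% | 0.008 (13%) | about 15% |
| 45% / 25% | 27% / 14% | 0.025 (40%) | about 45% |
| 22% / 12% | 13% / 7% | 0.047 (77%) | about 75% |
| 35% / 35% | 21% / 18% | 0.058 (94%) | over 90% |
| 25% / 45% | 16% / 22% | 0.090 (146%) | about 145% |

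**Absolute bias.** With unequal rates it is about 0.01 to 0.05 SD. If the link were 0.20 SD per week, the 45%/25% case gives 0.120 − 0.048 = 0.072 SD and the 50%/20% case 0.123 − 0.019 = 0.104 SD. These are 21% and 31% of the 0.34 detectable effect.

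**With app use added to the missing-data model only.** The estimates become 0.059 of 0.060 SD (45%/25%), 0.060 of 0.059 (50%/20%) and 0.064 of 0.063 (equal 35%). A separately coded simulation recovers 97% to 105% whenever some stoppers answer. If no stoppers answer, the effect is not identifiable. If use is instead made a covariate in the effect model, the coaching estimate falls to about zero, because the model then conditions on the mediator.

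**The case against.** The strongest objection is that everything turns on response rates the documents do not give. That stands. A reader might infer that most of the coaching benefit would be lost; this follows only from a sizeable gap between groups in the assumed rates. The 20% dropout in 6.5.1 is no anchor, because it belongs to the single-arm field trial in which everyone had access to coaching. For the RCT the only hint is 300 enrolled against 270 powered. If that is an allowance for loss, it is 30/300 = 10%, which is roughly the 22%/12% row, where about three quarters is kept.

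A reader might also infer that the bias always runs toward no effect. The last row of the table shows that it need not. Several provisions could narrow or close the gap: assessments are paid for and app use is not, coaches do not assess their own participants (4.1.6.1), follow-up may continue after withdrawal from treatment (4.4.1), and the retention contact in 4.1.7 is not limited by group. Against this, 4.4.3 lists inability to comply as a reason to end follow-up.

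A third tempting reading is that a null symptom result would be caused by the missing scores. It would not. With 150 coached and 150 uncoached, the standard error is √(2/150) = 0.115 SD, so complete data would give only about 8% power for 0.06 SD. The 45%/25% bias of about 0.035 SD is under a third of a standard error.

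Finally, 6.11.1 does not exclude app use; it lists no covariates at all. But its silence leaves the default model, and the one stated use of mediators in the RCT models, as time-varying covariates, would be the wrong remedy here.

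**Conclusion.** The point holds as a conditional weakness with an inexpensive remedy. The mixed model in 6.11.1 protects the coaching contrast only if response does not depend on app use beyond group and observed scores, and the protocol's own premises give reason to doubt that. The direction depends on which group's stoppers respond less.

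On the 0.10 SD per week drawn from 6.9.2, unequal response costs or adds about 0.01 to 0.05 SD; equal response at moderate rates costs almost nothing. A bias near 0.10 SD needs a link twice as strong. These sizes rest on assumed response rates, exponential times, the 7 and 10 weeks applied to coaching, and a linear causal reading of an effect size whose source section (D.1.1) is not in the documents. They show how sensitive the analysis is and do not predict this trial's bias.

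**What to change.** In 6.11.1:

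1. Multiply impute missing scores separately within the four randomised groups. Use the baseline score, the other visit scores and app use up to each visit (weeks used, time of last use) as predictors.
2. Fit the planned mixed model to the imputed data and combine with Rubin's rules. Keep app use out of the effect model, so that the contrast remains a comparison of everyone randomised.
3. Report the plain mixed model alongside.
4. Report questionnaire completion at each visit by group and use status.
5. Add a delta-adjusted sensitivity analysis for stoppers' missing scores. Imputation within groups cannot help if stoppers rarely or never answer.
6. Reconcile the outcome list with 4.3.1.1.2.1 so that the status of GAD-7 is clear.

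The cost is analysis work on data already collected, an imputation model to specify in advance, and a very small loss of precision: at 150 per group the SD of the estimate was 0.129 with app use against 0.126 without. If non-response proves equal across groups, the answer will change little.

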#### 4.3 Data

- **4.3.1.1.1** *Adherence:* The primary adherence outcome will be length of time from initiating treatment to last use of treatment elements. We will also explore the motivational system by examining the number of motivational messages delivered, number viewed and the ratio of viewed/delivered by treatment arm. More specifically:
- **4.3.1.1.1.1** Messages include text and email messages between participants and study staff for the purposes of coaching and participant management.
- **4.3.1.1.2** App use includes the number, timing, and duration, application launches and launches of specific pages within the app.

- **4.3.1.1.2** *Depression:* Primary patient centered outcomes will use continuous measures of depression and anxiety.
- **4.3.1.1.2.1** *PHQ-9* will be used to evaluate self-reported depression. GAD-7 will be used to evaluate self-reported anxiety.
- **4.3.1.1.3** *Secondary Outcome Measures* will include the following (for a full list of self-report measures see Measures Appendix):
- **4.3.1.1.3.1** *Satisfaction*, measured using the USE questionnaire, which was designed to measure satisfaction, usefulness, ease of use, and ease of learning.

*Moderators and mediators* will include the measures provided prior to initiating treatment the Mini International Neuropsychiatric Interview, the SCT Motivation assessment, Behavioral Activation, wellbeing and quality of life, Coping, and

**4.3.1.1.3.2** Audiofiles include audio recordings of coaching and assessments. Audio files may be transcribed by one or more of the following NU transcription vendors:

GMR Transcription https://www.gmrtranscription.com/

Wordsworth https://wordsworthcoop.com

Files may be shared via secure access to FSM servers or through vendors' proprietary web-based applications for secure file management.

- **4.3.1.1.4** Coach generated notes on participant encounters.
- 4.4 Removal of Subjects from Study

Patients can be taken off the study treatment and/or study at any time at their own request, or they may be withdrawn at the discretion of the investigator for safety, behavioral or administrative reasons. The reason(s) for discontinuation will be documented and may include:

- 4.4.1 Patient voluntarily withdraws from treatment (follow-up permitted);
- 4.4.2 Patient withdraws consent (termination of treatment and follow-up);
- 4.4.3 Patient is unable to comply with protocol requirements; (termination of treatment and follow-up);

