### **6** STATISTICAL CONSIDERATIONS

- **6.1** Public Deployment
- **6.2** Adherence Outcomes:
- 6.3 The primary outcome of Phase 1a will be rate of usage of each Intellicate application. This will be

examined by calculating standard descriptive statistics for the number of downloads and launches of each application. Secondary analyses of the primary outcome will include comparisons of co-usage of Intellicare application pairs, which we will test using Pearson correlations.

- **6.4** Field Trial
- **6.5** Power/sample size:
- 6.5.1 We estimate that we will have a 20% dropout, which will give us 80% power to detect effect sizes of 0.30. Power calculations were performed using Pass 2008.(Hintze, 2008)
- **6.6** Adherence Outcomes:
- 6.6.1 The primary outcome will be time to last use of a treatment element (lesson or tool), and will be tested between groups using traditional survival (Kaplan-Meier) methods, where the event of interest is last use from intervention start. Secondary analyses of the primary outcome would include Cox regression models that would adjust for potential effect modifiers or moderators such as gender, race, and age.
- **6.7** Patient Centered Outcomes:
- 6.7.1 Although power was presented for independent t-tests, primary analyses for patient centered outcomes (PHQ-9 and GAD-7) will utilize dependent t-tests
- **6.8** Mediation Analyses:
- 6.8.1 Mediators, such as app usage, we be examined in mediation models as time-varying covariates. We used the framework of Muller and colleagues(Muller, Judd, & Yzerbyt, 2005) to identify those variables, which mediate the effects of treatment on depression and anxiety. Only if the 4 criteria specified by Muller are satisfied (treatment effect for depression, treatment effect for the mediator, effect of mediator on depression, and reduction of treatment effect when mediator is included), will we calculate the effect of mediation using MacKinnon and colleagues' product of coefficients method.(MacKinnon, Lockwood, Hoffman, West, & Sheets, 2002) Bias-corrected 95% confidence intervals for the mediated effect will be calculated using bootstrapping.(Shrout & Bolger, 2002)
- 6.8.2 Development of the recommendation engine algorithms will use machine learning and Baysean. statistical methods that will continuously learn that will continuously learn from user interactions with IntelliCare to provide intervention recommendations.
- **6.9** Randomized Control Trial
- **6.9.1** Power/sample size:

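### The mediation plan fixes no time order between mediator and symptoms and does not adjust for earlier symptoms, so a variable that merely follows mood can be reported as a mediator

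*Combined protocol and SAP*

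**What the plan says.** Section 6.12.1 (randomised trial): "Mediators will be entered into our models as time-varying covariates". Section 6.8.1 (field trial) has the same approach and names one mediator: "Mediators, such as app usage, we be examined in mediation models as time-varying covariates".

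In both sections the mediated effect is estimated only if four criteria hold: a treatment effect on depression, a treatment effect on the mediator, and then "effect of mediator on depression, and reduction of treatment effect when mediator is included". Uncertainty is handled as follows: "Bias-corrected 95% confidence intervals for the mediated effect will be calculated using bootstrapping".

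Objective 2.2.1 gives the candidates. They include use of the apps, "Exploration of the mediating effects of adherence markers (e.g. time in treatment, app launches, etc", coaching variables such as message frequency and timing, and "psychological variables (e.g. change in self-report measures) on depression and anxiety outcomes".

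Two other places bear on timing. Section 4.1.6.1 gives the outcome schedule: "Self-reported depression will be measured at baseline, wk4, wk8, 3 months post-treatment and 6 months post-treatment using the PHQ-9 administered online". GAD-7 follows the same visits. Section 4.3 says that app-use data include timing and duration, but it also says that moderators and mediators "will include the measures provided prior to initiating treatment".

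**The concern.** App launches, time in treatment and changes in self-report can all plausibly respond to mood. People may stop using an app because they feel better, or because they feel worse. A model that relates the mediator to the outcome with no order between them, and with no earlier symptom score, cannot tell mediator-to-mood from mood-to-mediator. None of the four criteria tests direction, and the bootstrap interval covers sampling error only.

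Mediation is the analysis that would examine the link the trial is built on. Section 6.9.2 assumes that three more weeks of participation would bring an 11% improvement in depression severity. If use merely tracks mood, the analysis could appear to confirm that link when it is absent.

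**Working it through.** **The plan's own figures.** The mediation sections state none. The illustration borrows the trial size and continuous-outcome effect from section 6.9.2: 135 per arm, 80% power at an effect size of 0.34. Check: n per arm = 2 × (1.960 + 0.842)² / 0.34² = 135.8, so 136. Power at 135 per arm is 79.8%. The figure reproduces.

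**What the sections leave open.**

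| Item | 6.12.1 | 6.8.1 |
|---|---|---|
| Mediator enters as | time-varying covariate | time-varying covariate |
| Same visit, earlier visit or preceding interval | not stated | not stated |
| Adjustment for earlier symptoms | none | none |
| Reverse-direction check | none | none |

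**Closed form for a pure consequence, same-visit entry.** Let Y be the symptom score (SD 1 within arm), τ the treatment effect on Y, and M = rY + noise (SD 1). M has no effect on Y. Then:

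- treatment to mediator: a = rτ
- mediator to outcome, given treatment: b = r
- apparent mediated share: ab/τ = r²

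For r = 0.30, 0.45 and 0.60 the share is 9%, 20% and 36%, when the truth is 0%. The share is positive whether better mood raises or lowers the mediator, because a and b change sign together.

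**How often the criteria let it through.** The mediator-outcome path alone is significant almost always. The binding criteria are the two treatment effects. With τ = 0.30 and 135 per arm, SE = √(2/135) = 0.122.

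- Treatment effect on depression: 0.30/0.122 = 2.46, so power is about 69%.
- Treatment effect on the mediator: rτ = 0.090, 0.135 and 0.180, which divided by 0.122 give 0.74, 1.11 and 1.48. Power is about 11%, 20% and 32%.

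Simulating this single-visit model, all four criteria were met in about 10%, 18% and 29% of trials (any shrinkage of the treatment effect counted as a reduction).

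**Two-visit version.** 135 per arm; weeks 4 and 8; treatment acting directly on mood (0.34 SD at week 8, 70% of that at week 4); baseline-adjusted model with exchangeable covariance; true mediator effect zero; 1,000 runs per setting. Monte Carlo intervals for the product of coefficients stood in for the bootstrap.

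| Mood-mediator correlation (size) | Four criteria met and interval excludes 0 | Mean apparent share |
|---|---|---|
| 0 | 0.1% | 0% |
| 0.16 | 5.7% | 2% |
| 0.31 | 14.2% | 8% |
| 0.48 | 26.2% | 18% |
| 0.66 | 51.6% | 37% |

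At 150 per arm (section 4.1.6 has four groups of 75, so two groups per factor level) the last three rates are 14.4%, 31.1% and 53.6%.

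**Does ordering cure it?** In the same simulations, the week-4 mediator was used for the week-8 outcome:

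- Lag only: the interval excluded 0 in 0.5%, 2.5%, 8.6% and 25.7% of runs at correlations 0.16 to 0.66.
- Lag, with the week-4 outcome added to the outcome model: estimated effect about 0, and the interval excluded 0 in at most 0.8% of runs.

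A separate simulation of app use in the interval before the outcome (270 participants, correlations 0.30, 0.45 and 0.60) showed the same pattern. The interval excluded 0 in 4%, 11% and 23% of runs without adjustment for start-of-interval mood, and in about 0.1% with it. Power for real within-interval mediation stayed near 90% in that set-up, a figure that depends on the assumed strength of the mediation. Order alone is therefore not enough; the earlier symptom score is what removes the artefact.

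**The case against.** The plan does not say that mediator and outcome come from the same visit. A time-varying covariate may be lagged, cumulative or interval-based, and logged app use attached to a visit would naturally be use before it. A reader might infer that same-visit entry is the stated choice; the documents do not support that. What stands is that the plan permits it, and that even prior-interval use needs the symptom adjustment that the plan omits.

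A reader might also infer, from the near-certain significance of the mediator-outcome path, that a pure consequence will be declared a mediator. It usually will not be, because the treatment effects on depression and on the mediator must also be significant. Except at the strongest correlation examined, most such variables fail. They still pass far more often than under zero correlation (0.1%).

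Nor do the documents show that self-report mediators are collected at the PHQ-9 and GAD-7 visits. Section 4.1.6.1 does not schedule them by name, and section 4.3 calls them pre-treatment measures. Such measures cannot be caused by later improvement. But random assignment cannot change them either, so they cannot be mediators or vary over time. This is an inconsistency to resolve, not a safeguard.

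Finally, the section is headed secondary and the objective is exploratory. That stands, and it limits the importance of the point.

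**Conclusion.** The concern holds in this form: temporal order and adjustment for earlier symptoms are missing, and the criteria cannot supply them. With no true mediation and same-visit entry, the false-pass rate is roughly 10% to 30% at correlations of about 0.3 to 0.6, and about 50% at 0.66 in the two-visit version. The apparent mediated share is about 9% to 36%. These figures rest on assumed correlations, on treatment effects of 0.30 to 0.34 SD, and on mood driving the mediator at the same visit. They do not carry over to the field trial, which has a single arm, although its wording leaves the same gap.

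A reader might infer that the trial's main conclusions are at risk, or that objective 2.2.1 is defeated. Neither follows. The randomised comparisons, primary outcomes and sample size do not depend on this analysis, and an exploratory aim can tolerate some ambiguity if it is labelled. This is a desirable improvement, not an essential one.

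**What to change.** In 6.12.1, and in 6.8.1 as far as a single-arm phase allows, replace the sentence on time-varying covariates with wording such as:

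> App-use and messaging mediators will be taken from logs covering the interval before each outcome assessment. Both the mediator model and the outcome model will adjust for PHQ-9 and GAD-7 at the start of that interval (baseline for week 4, week 4 for week 8). Self-report mediators will be taken from the previous assessment, with the same adjustment, where they are collected then. Otherwise same-visit results will be reported as associations and not as mediation.

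Adjust also for the baseline mediator where there is one, and add a reverse-direction sensitivity analysis (earlier symptoms predicting later mediator).

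Reconcile section 4.3 with 2.2.1 and 6.12.1: separate pre-treatment moderators from mediators measured after randomisation, and state when each mediator is collected.

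The cost is SAP wording and data preparation. PHQ-9 and GAD-7 at baseline, week 4 and week 8, and time-stamped app logs, are already planned. The statistical price is fewer usable time points, somewhat wider intervals and, for self-report mediators, no credit for mediation already expressed at the earlier visit. The change does not make the mediator randomised: mood shifts within an interval, and unmeasured common causes, can still bias the estimate and should be stated as limitations.
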